POLYVAC	AC Center for Research and Production of Vaccines and Biologicals		
PPMC	Provincial Preventive Medicine Center		
SRC	Safety Review Committee		
RBC	BC Red Blood Cell		
RCR	RCR Responsible Conduct of Research		
RNA	Ribonucleic Acid		
RT-PCR Reverse Transcription Polymerase Chain Reaction			
RV	Rotavirus		
SAE	Serious Adverse Event		
SD	Standard Deviation		
SDV Source Data Verification			
SOP	SOP Standard Operating Procedure		
TCID	Tissue Culture Infectious Dose		
US	US United States		
VND	Vietnamese Dong		
VP	Viral Protein		
WHO	World Health Organization		
WIRB	Western Institutional Review Board		

Title:	A Phase III, Randomized, Partially Double-Blind, Active Control Study to Compare the Immunogenicity and Safety of a Liquid Formulation of ROTAVIN with the currently Licensed Frozen Formulation of the Vaccine (ROTAVIN-M1), in Healthy Vietnamese Infants.	
Description of Study Design:	 The study is designed as a phase III, randomized, double-blinded, active controlled study with two groups of infants receiving vaccines at the ratio of 2:1 (550 participants receiving the liquid formulation of ROTAVIN and 275 participants receiving the frozen formulation ROTAVIN-M1), to compare their immunogenicity and safety. Two doses of vaccine will be administered 8 (+2) weeks apart (minimum interval of 8 weeks and maximum of 10 weeks), with the first vaccine administration at 60-91 days (both days inclusive) of age. Active surveillance for vaccine reactogenicity (solicited reactions) over the 7-day period after each vaccination, unsolicited AEs for 4 weeks after each vaccination and SAEs including intussusception over the period between first vaccination and four weeks after the last vaccination will be conducted for all infants. Immunogenicity will be assessed in all subjects enrolled at one of the two proposed sites. Blood samples will be collected from all the participating infants from Quang Ninh site before the first and four (+2) weeks after the second vaccination to evaluate immune responses to rotavirus vaccine. 	
Hypothesis:	The study hypotheses are that:	
	Immunogenicity: Liquid formulation of ROTAVIN manufactured under full MOH Regulatory compliance is as immunogenic as the currently licensed frozen formulation of the vaccine (ROTAVIN-M1) Safety: Liquid formulation ROTAVIN manufactured under full MOH Regulatory compliance is safe and well tolerated	
Study Objectives	Primary Objectives	
Study Objectives	Immunogenicity	
	To demonstrate non-inferiority in the immunogenicity of the liquid formulation of ROTAVIN in comparison to currently licensed frozen formulation of the Vaccine (ROTAVIN-M1), 28 days after the last dose of the vaccine when administered to infants in a two-dose schedule starting at 60-91 days of age.	
	Safety	
	To evaluate the safety of liquid formulation of ROTAVIN in comparison with currently licensed frozen formulation (ROTAVIN-M1), in terms of solicited reactions after each dose of vaccine.	
	Secondary Objective	
	Immunogenicity	

PROTOCOL SUMMARY

	To further characterize the immunogenicity of the liquid formulation of ROTAVIN in comparison with currently licensed frozen formulation of				
	the Vaccine (ROTAVIN-M1).				
	Safety				
	To evaluate the safety of the liquid formulation of ROTAVIN in terms of immediate post-vaccination events, unsolicited adverse events and serious adverse events, including monitoring for intussusception.				
Study Endpoints	Primary Endpoint:				
	Immunogenicity				
	Rotavirus vaccine immunogenicity will be tested on serum samples obtained in a subset of 450 participants before the first vaccination and four weeks after the second vaccination using a validated ELISA assay. The primary immunogenicity endpoint is as follows,				
	• Geometric mean concentration (GMC) of serum anti-rotavirus IgA antibody concentrations 28 days after the second vaccination.				
	Safety:				
	Solicited post-vaccination reactogenicity (fever, diarrhea, vomiting, decreased appetite, irritability, and decreased activity level) during the 7 day period (Day 1-7) after each vaccination				
	Secondary Endpoint:				
	Immunogenicity				
	• Percentage of participants with seroconversion in serum anti- rotavirus IgA antibody concentrations 28 days after the second vaccination.				
	 o For participants with a negative pre-vaccination IgA concentration (< 20 IU/ml), a positive post-vaccination IgA concentration (≥ 20 IU/ml); 				
	• For participants with a positive pre-vaccination IgA concentration, a post-vaccination IgA concentration at least 4 times as high as the pre-vaccination IgA concentration.				
	• Percentage of participants with seropositivity at baseline and 28 days after the second vaccination. Seropositivity is defined as serum IgA antibody concentration ≥ 20 IU/ml.				
	Safety				
	 Immediate adverse events, within 30 minutes after each vaccination. Unsolicited AEs from vaccination through four weeks after each dose. 				
	• Serious adverse events (SAEs) and intussusception from first vaccination through four weeks after the last vaccination.				
Study Population:	Approximately 825 healthy male or female infants, aged 60-91 days (both days inclusive) at the time of enrollment.				
Phase:	Phase III				

Number of Sites:	2 site. The study will be conducted by National Institute of Hygiene and Epidemiology (NIHE) at Nam Dinh and Quang Ninh provinces, Vietnam		
Study Duration: Approximate duration of clinical phase of the study is estimated months whereas the total duration including analysis and reproximately 18 months.			
Participation Duration:	Approximately 3 – 4 months per participant		
Description of Agent or Intervention:	Test VaccineROTAVIN liquid formulation:Live Attenuated human rotavirus vaccine at a dosage of $\geq 2x10^6$ PlaqueFocus Units (PFU) / Dose of 2 ml. The vaccine can be stored and transported at 2-8 °C. The vaccine is for oral use.Comparator vaccineROTAVIN-M1:Live Attenuated human rotavirus vaccine at a dosage of $\geq 2x10^6$ PFU / Dose of 2 ml. The frozen vaccine vial will be stored at -20°C. The vaccine can also be stored and transported at 2-8 °C up to 2 months. The vaccine is for oral use.		
Estimated Time to Complete Enrollment:	Full enrollment for the study is anticipated within 7 months of first vaccination.		

Visit	V1*		V2*	V3
Time point (Day)	D1		D57	D85
Interval	Screening	Post- enrollment	V1+ 8 (+2) weeks	V2+ 4 (+2) weeks
Information process and written informed consent	Х			
Collect baseline demographic data	Х			
Collect/review medical history	Х			
Perform Physical examination and Vital examination	Xª		Х	Х
Check inclusion/exclusion criteria	Х			
Enrollment	Х			
Randomization		Х		
Collect blood for immunogenicity assessment ^b		X (Pre-dose)		Х
Check withdrawal criteria			Х	Х
Check contraindications, warnings and precautions to vaccine administration			Х	
Study vaccination		Х	Х	
Observe for immediate reactions for 30 minutes		Х	Х	
Perform post-vaccination Vital examination and targeted physical examination if required.		Х	Х	
Issue and instruct parent/LAR of participant on use of diary card		Х	Х	
Record solicited AEs within 7 days post-vaccination		Х	Х	
Safety follow-up by health worker ^c		Х	Х	
Record unsolicited AEs , including SAEs		Х	Х	Х
Record any concomitant medications/vaccinations		Х	Х	Х
Review interim medical history and record any intercurrent medical conditions			Х	Х
Participant completion of study				X

Table 1: Trial Schema- Schedule of Events

D = day; AE = adverse events; SAE = serious adverse event; Shading represents days of vaccination; V = Visit number.

* The study visits will be planned in advance such that the EPI vaccination days fall either 7 days before or after the study vaccination day. This will allow the participant to receive EPI vaccines in the window allowed by the protocol.

^a Symptom based PE to be performed if screening is being repeated and there is any change in health since last screening.

^bAt Quang Ninh site

^c This includes visit by the health worker to the participant's home on Day 2/58(+1) and 8/64(+2) after each vaccination and a telephone call on Day 5/61 (+2).

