The phase 1 study was conducted in Thanh Son district, Phu Tho province of Viet Nam. For the study 29 healthy adult volunteers 18–49 years of age were enrolled after a thorough screening which included baseline blood sampling to test for hematological and biochemical parameters. All volunteers were administered 2 doses of the high titer vaccine, $10^{6.3}$ PFU/2ml at a 1-month interval. The volunteers were followed daily for 10 days for adverse events and for fecal sample collection after administration of each dose of the vaccine. Volunteers were followed up by phone for the next 20 days. Serum samples taken before and 30 days after the 1st and 2nd doses were tested for blood counts, BUN concentration and serum transaminase levels. During the 30 days post-vaccination of each dose, no diarrhea or severe adverse reaction was reported by any of the volunteers. No change in blood counts or BUN concentration was observed at any of the post vaccination sampling time points. Serum transaminase levels stayed below 40 IU/ml for >85% of volunteers or slightly elevated (42-56 IU/ml) in 10% of volunteers after 2 doses of vaccine. One volunteer had elevated levels of both SGOT and SGPT (71 and 48 IU/ml, respectively) before vaccination and the levels remained in this range after 2 doses of vaccine. Overall, two doses of ROTAVIN-M1 higher dose (10^{6.3} PFU/dose) were well-tolerated in adults. No shedding of the vaccine virus occurred in these adults following vaccination. Data on the volunteers were reviewed by the Data and Safety Monitoring Board (DSMB). The DSMB judged the vaccine to be safe, permitting the phase II study to start in infants.

Phase II study in infants

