7.2 Second Vaccination (Day 57; +14 days)

The date for this visit will be calculated 56 days from the date of the first study vaccination. A maximum window period of +14 days will be allowed for this visit. Parents will be contacted by phone few days before the visit to remind them of the appointment. Participants who miss the scheduled visit date will be prompted to re-schedule for the missed visit. The following procedures will be carried out at this visit:

- 1. Study staff will confirm participant's identity.
- 2. Check for any adverse events since last visit and record them in the source note and eCRF if applicable. Update medical history including follow-up of prior AEs.
- 3. Collection and review of the diary cards if not already collected by field worker earlier.
- 4. Check for use/administration of any medication/vaccine since last visit. Any medication taken for the treatment of the illness or vaccine administered will also be recorded in the relevant section of the CRF.
- 5. Conduct physical examination and vital examination and record the information on the CRF. Results will be reviewed by study staff and discussed with the parent. Any AEs that have occurred will be recorded in the appropriate section(s) of the CRF.
- 6. Check for any contraindication to vaccination. Reschedule visit if the infant is experiencing an illness that is temporary contraindication to vaccination.
- 7. Vaccines will be administered by an unblinded study staff if participant does not meet any contraindication to Investigational Medicinal Product (IMP) administration. The participant will receive a dose of vaccine bearing the same randomization code as for visit 1. A section of study eCRF will be completed that records information about vaccines received, date and time.
- 8. Procedures 5-7 under section 7.1 above will be repeated.

9. Remind the parent of the safety follow up visit and phone call by the field officer and advise him/her on the next clinic visit after 28 days.

Safety Follow-Up

- 1. Participants parent/LAR will complete the Diary Card daily, reporting solicited reactions experienced and medications taken from the evening of D57 through D63 after vaccination.

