In this study only systemic solicited events of fever, diarrhea, vomiting, decreased appetite, irritability, and decreased activity level will be monitored. Local reactions to EPI vaccination should be reported as unsolicited AEs.

Unsolicited AEs are any AEs reported spontaneously by the participant's parent/LAR, observed by the study personnel during study visits or those identified during review of medical records or source documents. Unsolicited AEs are not specified for active monitoring, but spontaneously reported as untoward events occurring in a participant. All such events will be recorded on the 'Adverse event' pages of the eCRF.

SAEs are defined in Section 9.9.

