9.8 Unsolicited Adverse Events

Unsolicited adverse events are any AEs that occur any time after the study vaccine is given (temporally related to study product), whether or not deemed "related" to the product, and are not solicited. Unsolicited AEs can be observed by study staff while the participant is at a clinic for a study visit or reported by the participant's parent/LAR at any time. Unsolicited adverse events will be recorded with onset from the time of vaccination up to 28 days after each vaccination. Any solicited sign or symptom starting after 7 days post vaccination will be recorded as an "unsolicited AE".

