Vaccinated participants will be observed for immediate adverse events for 30 minutes after each vaccination. Active surveillance for vaccine reactogenicity (solicited reactions) over the 7-day period after each vaccination, unsolicited AEs for 4 weeks after each vaccination and SAEs including intussusception over the period between first vaccination and four weeks after the last vaccination will be conducted for all infants.

This study will have extensive safety monitoring in place. At the performing site level, the study site investigators and their clinical staff will be responsible for continuous close safety monitoring of all study participants and for alerting the protocol team if unexpected concerns arise. A team of vaccine experts, Safety Review Committee (SRC) composed of a group of physicians, which include but not limit to the designated investigator from study team and the Medical Officer(s)

from POLYVAC and PATH, a Pharmacovigilance/Medical officer from the CRO and an independent vaccine expert will be closely following the study for safety oversight. The SRC may seek independent expert medical opinion as dictated by the occurrence of certain events.

The SRC will have provision of expedited meeting that could be triggered by reporting of predefined AEs. The SRC may also seek independent expert medical opinion as dictated by the occurrence of certain events.

The schedule of study assessments is given in Table A1 below.

Table A1: Trial Schema- Schedule of Events

Visit	V1*		V2*	V3
Time point (Day)	D1		D57	D85
Interval (window period)	Screening	Post enrollment	V1+ 8 (+2) weeks	V2+ 4 (+2) weeks
Information process and written informed consent	X			
Collect baseline demographic data	X			
Collect/review medical history	X			
Perform Physical examination and Vital examination	X ^a		X	X
Check inclusion/exclusion criteria	X			
Enrollment	X			
Randomization		X		
Collect blood for immunogenicity assessment ^b		X (Pre-dose)		X
Check withdrawal criteria			X	X
Check contraindications, warnings and precautions to vaccine administration			X	
Study vaccination		X	X	
Observe for immediate reactions for 30 minutes		X	X	
Perform post-vaccination Vital examination and targeted physical examination if required.		X	X	
Issue and instruct parent/LAR of participant on use of diary card		X	X	
Record solicited AEs within 7 days post vaccination		X	X	
Safety follow-up by health worker ^c		X	X	
Record unsolicited AEs, including SAEs		X	X	X

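### Four weeks of active surveillance for unsolicited AEs is promised, but after Dose 1 no safety enquiry is scheduled between the Day 8 (+2) home visit and Visit 2 on Day 57 (+14)

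*Protocol*

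**What the plan says.** The Protocol Summary (Description of Study Design) promises "Active surveillance for vaccine reactogenicity (solicited reactions) over the 7-day period after each vaccination, unsolicited AEs for 4 weeks after each vaccination". Protocol Section 4 repeats this. SAP 4.1 places the same surveillance heading over "unsolicited AEs for 4 weeks after each vaccination and SAEs including intussusception over the period between first vaccination and four weeks after the last vaccination". The unsolicited AE window is therefore four weeks after each dose, while the SAE window is continuous.

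Protocol 9.1 describes unsolicited AEs differently: "Unsolicited AEs are not specified for active monitoring, but spontaneously reported as untoward events occurring in a participant". Protocol 9.8 fixes the window: "Unsolicited adverse events will be recorded with onset from the time of vaccination up to 28 days after each vaccination".

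For follow-up, Table 1 footnote c gives health-worker visits to the infant's "home on Day 2/58(+1) and 8/64(+2) after each vaccination and a telephone call on Day 5/61 (+2" days). Section 7.1 lists the same three contacts after Dose 1 and none later. The diary card covers Days 1-7. The next AE enquiry is in Section 7.2, at the second vaccination visit: "Check for any adverse events since last visit and record them in the source note and eCRF if applicable". Sections 7.2 and 7.4 also plan a telephone reminder shortly before that visit, with no AE question attached.

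**The concern.** Active surveillance normally means that staff go and ask. After Dose 1 they ask during the first 8 to 10 days and then not again until well after the 28-day window has closed.

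The unasked days are not empty:

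- Section 6.6 keeps EPI vaccines at least 7 days away from study vaccine, so any given soon after Dose 1 fall in this stretch.
- Local reactions to EPI vaccines count as unsolicited AEs (9.1), and so does a solicited symptom that starts after Day 7 (9.8).
- In the earlier Phase III trial of ROTAVIN-M1 (2.5.3), fever and irritability were the commonest AEs on Days 8-30 in the vaccine group. The protocol suggests routine vaccines as a reason. Separating the two sources needs good onset dates.
- Onset date also decides whether an event enters the four-week tables of SAP 13.2.2.

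At stake is the completeness of a secondary safety endpoint in a trial whose size was set by a regulatory requirement for safety data on 500 recipients of the new formulation. The SAP lays out the after-Dose-1 and after-Dose-2 tables identically, with no note that the information was gathered at different distances from the events.

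**Working it through.** **Inputs.** Dose 1 is Day 1 (7.1). The AE window is 28 days after each dose (9.8). Safety contacts after Dose 1 fall on Day 2 (+1), Day 5 (+2) and Day 8 (+2) (Table 1 footnote c). Visit 2 is 56 days after Dose 1, window +14 (7.2). Visit 3 is 28 days after the last dose, window +14 (7.3).

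**Step 1: the plan's own visit days.** Visit 2 = 1 + 56 = Day 57, latest 57 + 14 = Day 71. With Dose 2 on Day 57, Visit 3 = 57 + 28 = Day 85, latest Day 99. The nominal days agree with Table 1.

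**Step 2: window days after the last safety contact.** The Dose 1 window closes on 1 + 28 = Day 29.

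- Contact on Day 8: 29 - 8 = 21 of 28 days (75%).
- Contact on Day 10: 29 - 10 = 19 of 28 days (68%).

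After Dose 2 the share is the same: 85 - 64 = 21 and 85 - 66 = 19. The doses differ in the recall interval, not in the share of uncontacted days.

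**Step 3: time from event to next enquiry** (visit day minus event day).

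| Event | Dose 1: Visit 2 on Day 57 | Dose 1: Visit 2 on Day 71 | Dose 2: Visit 3 on Day 85 | Dose 2: Visit 3 on Day 99 |
|---|---|---|---|---|
| Last window day (Day 29 / 85) | 28 d (4.0 wk) | 42 d (6.0 wk) | 0 d | 14 d (2.0 wk) |
| Day after a Day 10 / 66 contact (Day 11 / 67) | 46 d (6.6 wk) | 60 d (8.6 wk) | 18 d (2.6 wk) | 32 d (4.6 wk) |
| Day after a Day 8 / 64 contact (Day 9 / 65) | 48 d (6.9 wk) | 62 d (8.9 wk) | 20 d (2.9 wk) | 34 d (4.9 wk) |

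Recall is therefore about 4 to 9 weeks after Dose 1 and about 0 to 5 weeks after Dose 2. For the same day after dosing and the same visit delay, the difference is always 28 days (for example 48 - 20 or 60 - 32).

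**Step 4: SAEs.** Their window is continuous, so the stretch without a scheduled safety enquiry is the whole interval from the last contact to Visit 2: 57 - 10 = 47 days at the shortest and 71 - 8 = 63 days at the longest (6.7 to 9.0 weeks).

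**Step 5: the reminder call.** It comes a few days before Visit 2 (7.2), hence after Day 29, and has no stated AE question. It does not shorten the intervals above.

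**The case against.** The strongest reply is that the plan does not depend on memory alone. Section 9.11 tells parents to contact staff at once, at any time, about any AE, not only one needing care. Section 7.5 allows unscheduled visits. Section 9.1 counts events found in medical records. The protocol never defines active surveillance as a contact frequency, and 9.1 could be read as merely separating diary-prompted events from unprompted ones. All of this stands, and it is why the gap is described here as parent-initiated reporting plus recall. But these routes wait for the parent or a record. They do not make the four weeks actively followed, and the two descriptions still have to be reconciled.

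Four stronger readings are tempting and are not supported:

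- **That there is no contact at all until Day 57.** The reminder call exists. What is missing is a scheduled safety enquiry.
- **That an SAE or intussusception would go unknown for weeks.** Nearby medical centres are informed of the study (2.7.1, 15.4), district and provincial facilities are under common management (Section 4), and parents are asked to give any provider the investigator's details (7.1). Late awareness is possible, but nothing in the documents shows that it is likely.
- **That a planned comparison is distorted.** Neither Protocol 12.4.3 nor SAP 13.2.2 tests Dose 1 against Dose 2, or one arm against the other, on unsolicited AEs. The analysis is descriptive, with Clopper-Pearson intervals.
- **That the loss can be sized.** A percentage would need an assumed event rate and assumed recall probabilities, and the documents give neither. Any such figure would also have to allow for the first 8 to 10 days, which are well covered and sit in the same tables.

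Misdated events are also not necessarily lost: Listing 15 marks those starting beyond four weeks. They would, however, drop out of the four-week tables.

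**Conclusion.** The point holds as an inconsistency in the documents with a modest effect on data quality. The Protocol Summary, Protocol Section 4 and SAP 4.1 claim active surveillance that Protocol 9.1 disclaims and the schedule does not provide. After Dose 1, 19 to 21 of 28 days (68-75%) have no scheduled safety enquiry, and recall runs 28 days longer than for the matching day after Dose 2.

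The expected consequence is under-ascertainment and poorer onset dating of non-serious unsolicited AEs after Dose 1. It should be similar in both arms, because they share the schedule and clinical assessors are blinded (5.2.2). The primary safety endpoint, solicited reactions on Days 1-7, is covered by the diary and three contacts and is unaffected. No planned test is biased.

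The day counts assume that visits fall within their windows and that the Day 8 visit finds the parents at home. Section 7.1 allows for their absence, and the gap would then be longer. That under-ascertainment follows from long recall is a judgement; its size cannot be derived from the documents.

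**What to change.** Either of two additions improves capture, and they can be combined:

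1. At the Day 8 home visit, leave a dated illness and medication page covering the rest of the 28-day window (to Day 29 on the count above), and review it at Visit 2.
2. Add one telephone enquiry at about Day 29 (+3) after Dose 1, made by blinded staff, asking about illness, medication and hospital visits since Day 8 and recording onset dates.

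Enter the change in Protocol Table 1 footnote c, Protocol 7.1 (Safety Follow-Up) and SAP Table A1, and reconcile 9.1 with the Protocol Summary, Protocol Section 4 and SAP 4.1.

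The cost is one printed page per infant or up to about 825 short calls, plus a minor amendment. Reported after-Dose-1 AE rates may rise slightly. There is a limited precedent in the Phase I trial (2.5.3): "Volunteers were followed up by phone for the next 20 days". That was in 29 adults, so it shows the method was used, not how well it works in infants.

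If neither addition is made, reword the surveillance statements for unsolicited AEs and SAEs in the Protocol Summary, Protocol Section 4 and SAP 4.1 to agree with Protocol 9.1. Also state in SAP 13.2.2 that after-Dose-1 and after-Dose-2 rates were collected with different recall intervals. That costs only text.
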